10.7 Participant population

- The pharmacodynamic analysis set will include all participants who achieve at least 80% compliance with study medication during each of the two periods and who complete both endotoxin injection days.
- The safety analysis set (for the purposes of adverse event reporting etc.) will include any participant randomised into the trial that received at least one dose of trial drug or one dose of intravenous endotoxin.

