- Vital signs at 1 hour and 1.5 hours post endotoxin injection
- Continuous IV infusion of 250 ml 0.9% saline over 1 hour
- 14 ml venous blood sample at 1 hour post endotoxin
- Urine sample at 1 hour post endotoxin
- 14 ml venous blood sample at 1½ hours post endotoxin

2 hours post-endotoxin injection

- Vital signs at 2 hours post endotoxin
- Continuous IV infusion of 250 ml 0.9% saline over 1 hour
- 23 ml venous blood sample at 2 hours post endotoxin
- Urine sample at 2 hours post endotoxin

3 hours post-endotoxin injection

- Vital signs at 3 hours post endotoxin
- 23 ml venous blood sample at 3 hours post endotoxin
- Bleeding time measurement at 3 hours post endotoxin

4 hours post-endotoxin injection

- Vital signs at 4 hours post endotoxin
- 14 ml venous blood sample at 4 hours post endotoxin
- Urine sample at 4 hours post endotoxin

6 hours post-endotoxin injection

- Vital signs at 6 hours post endotoxin
- 14 ml venous blood sample at 6 hours post endotoxin
- Urine sample at 6 hours post endotoxin
- Continuous cardiac monitoring ends

Visit 4 (Period 1, 1 day after visit 3)

- Telephone follow-up for adverse events
- Facility to convert to in-person visit if any concerns raised

There will then follow a washout period of at least 5 weeks, and not more than 18 weeks, between the first endotoxin challenge day and the beginning of the second medication period. This is to avoid reliably any tolerance of the response to endotoxin, a phenomenon absent by 5 weeks [39].

Visit 5 (10 to 14 days after visit 3)

- Telephone follow-up for adverse events

Visit 6 (Period 2, Day 0)

- Vital signs (BP, pulse, temperature)
- Physical examination
- Adverse event recording
- Concomitant medication recording
- Medically qualified investigator to confirm eligibility criteria again (see section 6) and that no withdrawal criteria (section 7.10) are met at this point prior to proceeding to medication period 2
- Laboratory safety blood tests: 12.5 ml venous blood for full blood count, urea & electrolytes (sodium, potassium, urea and creatinine), liver function tests, clotting screen
- Medication dispensed for period 2
- Dosing training for use of aspirin lysine if required

Participants will be advised to begin antiplatelet medication, allocated as follows, for period 2 from the morning after visit 6:

- If received no IMP in period 1, to receive no aspirin, but a loading dose of ticagrelor (180 mg) 1 hour before endotoxin injection in period 2.

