10 STATISTICS AND DATA ANALYSIS

10.1 Sample size calculation

In our group's previous study of endotoxaemia in 30 participants receiving ticagrelor, clopidogrel or placebo, we saw, after log transformation, a mean 2 hour post-endotoxin plasma TNF- α 1.88 pg/ml with a standard deviation of 0.410 pg/ml.

There is no available raw data and no reliable estimate of the means or standard deviations of the log transformed TNF- α values for any of the three aspirin doses using the same methods. However, a study using a different endotoxin regimen has shown that aspirin 80 mg OD (which is not expected to be significantly different in effect to 75 mg OD) increased peak plasma TNF- α by around 40% compared to those receiving no drug.

We have a clear hypothesis that increasing aspirin dose increases TNF- α , therefore a one-sided test will suffice.

We estimate that clinically-relevant differences in plasma TNF- α at 2 hours post-endotoxin between the dosing regimens might be a 20% increase with 20 mg BD vs. no aspirin, 40% increase with 75 mg OD vs. no aspirin and 60% with 300 mg OD vs. no aspirin, based on the raw data.

These assumptions provide the following sample size estimate:

Test significance level, α	0.050
Number of groups, G	4
Variance of means, $V=S(m_i-m)^2 / G$	0.031
Common standard deviation, s	0.410
Effect size, $D^2 = V/s^2$	0.1828
Power (%)	80
n per group	16

Therefore, when the sample size in each of the 4 groups is 16, a one-way analysis of variance will have 80% power to detect at the 0.050 level a difference in means characterised by a Variance of means, $V=\sum(\mu_i-\mu)^2 / G$ of 0.031, assuming that the common standard deviation is 0.410.

To allow for up to 10% drop-out, the sample size per group will be 18. Drop-outs will not be replaced but it is expected that there will be at least 16 per group after withdrawals.

This sample size calculation was performed by [name] CStat, Senior Consultant, Statistical Services Unit, University of Sheffield, to whom the investigators are grateful.

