10.6 Interim analysis and criteria for the premature termination of the trial

After discussion between the investigators and the Sponsor, face-to-face participant study visits were halted on 17th March 2020 due to the unprecedented circumstances arising during the coronavirus disease 2019 (Covid-19) pandemic. It was considered by the investigators that the results of the study may have important implications for the management of cardiovascular disease patients who contracted Covid-19 in terms of optimal antiplatelet medication, in view of the morbidity and mortality in Covid-19 associated with dysregulated inflammatory response. It was noted that the recruitment and study activities to date had reached the level that had originally been planned for the study, as per the application funded by the British Heart Foundation. Given the uncertainty regarding restarting the trial, the need to preserve healthcare resources and to limit face-to-face encounters, the investigators and Sponsor decided that an interim analysis should be performed.

Sample size for interim analysis

Data from all participants who have completed visit 3 (first endotoxin day) will be included in the interim analysis. This is expected to include 46 participants who have completed visit 3, 37 of whom have completed the whole study giving a total of 83 endotoxin day visits, anticipated to be split into approximately equal numbers receiving each of the eight study treatment regimens.

Statistical procedure for interim analysis

The primary endpoint of the interim analysis will be plasma TNF- α measured at 2 hours after endotoxin administration assessed between aspirin treatment groups (control vs. 20 mg BD vs. 75 mg OD vs. 300 mg OD, without ticagrelor) using one-way ANOVA.

Should this demonstrate a significant difference between the groups ($p<0.05$), the following pre-specified pairwise comparisons will be performed, in hierarchical fashion:

300 mg OD vs. no aspirin

then, if significant ($p<0.05$)

75 mg OD vs. no aspirin

then, if significant ($p<0.05$)

300 mg OD vs 20 mg BD

then, if significant ($p<0.05$)

75 mg OD vs 20 mg BD

then, if significant ($p<0.05$)

20 mg BD vs no aspirin

Other analyses will be exploratory.

Criteria for premature termination

The trial shall be prematurely terminated if the primary interim analysis demonstrates a statistically significant ($p<0.05$) effect of aspirin dosing on plasma TNF- α two hours after endotoxin injection.

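### The only non-safety analysis set requires both endotoxin days, although the primary test uses one visit, and it conflicts with the interim data set in section 10.6

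*Protocol*

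**What the plan says.** Section 10.7, identical in protocol and SAP, defines two sets. The pharmacodynamic set holds participants "who achieve at least 80% compliance with study medication during each of the two periods and who complete both endotoxin injection days". The safety set holds anyone randomised who received a dose of trial drug or endotoxin. Section 10.7 does not list the analyses that use the pharmacodynamic set, and section 10.3.2 names no set for the primary analysis.

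Section 10.3.2 makes the primary analysis a one-way ANOVA of 2-hour TNF-alpha across four parallel groups, without ticagrelor. Under section 7.3 each participant has one such visit, in period 1 for half of the eight sequences and in period 2 for the other half.

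For the interim, section 10.6 says "Data from all participants who have completed visit 3 (first endotoxin day) will be included in the interim analysis". It expects 46 such participants, 37 of them complete, and 83 endotoxin visits. For the analyses after early termination it asks for methods suited to participants with one period missing.

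Section 10.1 states that "when the sample size in each of the 4 groups is 16, a one-way analysis of variance will have 80% power to detect" the assumed effect, and continues: "To allow for up to 10% drop-out, the sample size per group will be 18".

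**The concern.** The set asks for more than the primary comparison uses. Someone allocated to the no-ticagrelor regimen first, who attends visit 3 and gives a 2-hour sample, has a complete primary endpoint. Section 10.7 removes that person if period 2 is never completed, or if compliance falls short in period 2, although the primary ANOVA uses nothing from period 2.

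The second problem is ambiguity. Section 10.6 admits participants with only one period, and 10.7 shuts them out. An analyst following 10.6 and one following 10.7 would run the interim ANOVA on different participants. That test decides whether the trial stops for a significant effect, and the futility limit for 300 mg OD against no aspirin comes from the same data. The population for a stopping decision should not be open to choice after the data are in hand.

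**Working it through.** **Inputs.** Alpha 0.05, four groups, and a variance of means V "of 0.031, assuming that the common standard deviation is 0.410" (section 10.1). Interim counts of 46, 37 and 83 (section 10.6). Planned total 72 with 10% drop-out (section 10.1). Equal allocation to eight sequences, half with the no-ticagrelor visit first (section 7.3).

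**1. The plan's own sample size.** Power is taken from the noncentral F distribution with 3 and N − 4 degrees of freedom and noncentrality λ = N × V/SD².

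- V/SD² = 0.031/0.410² = 0.1844. The plan's table gives 0.1828, which corresponds to V = 0.0307.
- At 16 per group, N = 64 and λ = 64 × 0.1844 = 11.8. Power is 0.806 (0.802 with 0.1828).
- At 15 per group power is 0.775 (0.771 with 0.1828), so 16 is the smallest adequate size.
- 16/0.9 = 17.8, rounded up to 18, and 4 × 18 = 72.

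The figures reproduce with the ordinary F test at 0.05, which has no direction, although section 10.1 says "therefore a one-sided test will suffice".

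**2. The interim conflict.** 46 + 37 = 83 visits, as section 10.6 states. Under 10.7 at most 37 participants remain, with 2 × 37 = 74 visits. The two sections differ by 9 participants and 9 visits.

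**3. Primary values at stake at the interim.** Each of the 37 completers has one no-ticagrelor visit. Of the nine with visit 3 only, those on a no-ticagrelor-first sequence also have a primary value. Section 10.6 expects roughly equal numbers on each of the eight regimens: 83/8 × 4 = 41.5 no-ticagrelor visits, so 41.5 − 37 = 4.5. The actual split is not given and could be anything from 0 to 9.

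| Primary values | λ | Power |
|---|---|---|
| 37 (10.7 governs) | 6.82 | 0.523 |
| 41 | 7.56 | 0.576 |
| 42 | 7.75 | 0.589 |
| 46 (all nine on no ticagrelor first) | 8.48 | 0.637 |

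For the expected 41.5, standard errors under 10.7 are larger by a factor of √(41.5/37) = 1.06.

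**4. Full trial.** Assume that all drop-out falls after visit 3 and that half of those who leave already hold a primary value. With drop-out d, the 10.7 set has 72(1 − d) values and the single-visit set has 72(1 − d/2).

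| Drop-out | 10.7 set | Power | Single-visit set | Power | Gain |
|---|---|---|---|---|---|
| 10% (planned) | 64.8 | 0.812 | 68.4 | 0.836 | 2.4 points |
| 20% (assumed) | 57.6 | 0.755 | 64.8 | 0.812 | 5.7 points |

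Drop-out before visit 3 narrows the gap, because those participants have no value in either set. All figures assume equal groups.

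**5. The compliance clause.** Controls take no daily drug, and their only trial drug is one observed ticagrelor dose (sections 7.3 and 8.11). The clause can therefore exclude people only in the three aspirin groups. However, section 7.10 already makes aspirin compliance below 80% a ground for withdrawal or postponement, section 7.7 has this checked before visits 3 and 7 proceed, and section 8.9 says the participant is withdrawn if the visit cannot be postponed. Anyone with a 2-hour value should already have passed the 80% rule for that period.

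**The case against.** The strongest reply is that section 10.6 is a specific rule for the interim and takes precedence over the general text of 10.7. On that reading no interim value is lost, and the defect there is a missing cross-reference. This is a fair reading. What stands is that neither document states it, and that 10.6 says nothing about the final analysis if the trial continues.

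It can also be said that an adherent set is a recognisable choice for a dose-effect question in healthy volunteers, and that paired comparisons need both visits. Both points are right. They support keeping the set for those purposes, but they do not justify tying the parallel-group primary test to a second visit.

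Three stronger inferences are tempting, and the documents do not support them:

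- **Bias from the compliance clause.** A reader might infer that 10.7 biases the dose comparison by filtering the aspirin groups against an unfiltered control. The clause is one-sided, but most of that selection occurs under 7.10 before endotoxin is given. The clause itself removes few further measured values, and redefining the set leaves the earlier selection in place.
- **The nine as drop-outs.** A reader might set 9 of 46 against the planned 10%. The nine were counted when visits were halted, in a design with a "washout period of at least 5 weeks, and not more than 18 weeks". Some or all may have been awaiting period 2.
- **A shortfall below 16 per group.** This requires all nine to be lost, 46 to be the number randomised so far, and 10% loss among the other 26: 37 + 0.9 × 26 = 60.4, with power about 0.78. In the same scenario the single-visit set has about 65 to 66 values and power of 0.81 to 0.82. The part due to 10.7 is about 4 points.

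**Conclusion.** The point holds in two respects. As written, 10.7 discards valid primary values for reasons unrelated to the primary comparison. It also conflicts with 10.6 by 9 participants and 9 visits, with no rule of precedence for a test that can end the trial.

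The size is modest. If 10.7 governed the interim, about 4 to 5 of 41 to 42 primary values would go. At the planned 10% drop-out the present set still reaches the 80% target, so the sample size is not in error.

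The power figures take the plan's V and SD at face value and assume equal groups, with an even sequence split among participants who have one visit. The conflict between 10.6 and 10.7 rests on none of these assumptions. It does rest on treating the pharmacodynamic set as the intended set for the primary test, which is an inference from its being the only non-safety set.

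**What to change.** In section 10.7 of both documents, define the primary analysis set as all randomised participants with a 2-hour TNF-alpha value at their no-ticagrelor endotoxin visit, analysed as randomised, whether or not the other period was completed and with no further compliance condition. Name this set in section 10.3.2 and in the interim procedure of 10.6, use it at both interim and final analysis, and state that it reconciles 10.6 with 10.7. Include every completed visit in the mixed-model secondary analyses. Keep the present 10.7 set for the paired comparisons with and without ticagrelor, and as a sensitivity analysis of the primary endpoint.

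The cost is wording only; no visit, sample or procedure changes. A few less-adherent visits may enter the primary analysis, and the sensitivity analysis would still report the adherent result. The change should be fixed before anyone sees TNF-alpha results by group.

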10.8 Procedure(s) to account for missing or spurious data

- Missing data will be recorded by notating 'NR' (not recorded) in the relevant section of the CRF
- Where analysis is performed using ANOVA, missing data will be estimated by multiple imputation using the IBM SPSS software package. Sensitivity analyses will be carried out to report the robustness of this approach.

10.9 Other statistical considerations.

Not applicable to this study

10.10 Economic evaluation

Not applicable to this study.

11 DATA MANAGEMENT

11.1 Data collection tools and source document identification

Source data will be recorded on the study-specific paper case report form (CRF). Source data will feed from the CRF to the trial master database..

A paper trial master file will be kept within the Cardiovascular Research Unit at the University of Sheffield, maintained by the Research Co-ordinator.

11.2 Data handling and record keeping

The investigators will maintain SOPs for the use of the CRF and database, maintain an audit trail of data changes ensuring that there is no deletion of entered data, maintain a security system to protect against unauthorized access, maintain a list of the individuals authorized to make data changes, maintain adequate backup of the data, and archiving of any source data (i.e. hard copy and electronic). This will include a clear record of data changes if transformed during processing. The investigators will use an unambiguous participant identification code that allows identification of all the data reported for each participant. All electronic data will be kept securely stored on University of Sheffield systems, or external handlers contracted by the University of Sheffield for this purpose. The Sponsor will be responsible for ensuring compliance with the requirements outlined above.

11.3 Access to Data

Direct access will be granted to authorised representatives from the Sponsor, host institution and the regulatory authorities to permit trial-related monitoring, audits and inspections in line with participant consent.

11.4 Archiving

Archiving will be authorised by the Sponsor following submission of the end of trial report. The sponsor will archive all study documents through existing SOPs and external contracts for a minimum of 15 years after the end of the study, as per local protocols. Destruction of essential documents will require authorisation from the Sponsor. The trial database will be kept by the investigators for at least 15 years, at which point storage arrangements will be reviewed, in electronic format on University of Sheffield file storage systems. This will be stated in the PIS.

12 MONITORING, AUDIT & INSPECTION

- A Trial Monitoring Plan will be developed and agreed by the Trial Management Group (TMG) and CI based on the trial risk assessment, which may include on-site monitoring. This will be dependent on a documented risk assessment of the trial by the Sponsor.
- It is anticipated that monitoring audits will take place after the first participant first visit and last participant last visit.
- The monitoring plan will be kept in the trial master file.
- The monitoring personnel will be determined by the Sponsor.
- The processes reviewed will include participant enrolment, consent, eligibility, and allocation to trial groups; adherence to trial interventions and policies to protect participants, including reporting of harm and completeness, accuracy, and timeliness of data collection.
- Monitoring will be performed through site visit to review original documentation.
- The investigators will host the site visits.

13 ETHICAL AND REGULATORY CONSIDERATIONS

13.1 Research Ethics Committee (REC) review and report, and Health Research Authority (HRA) approval

- Before the start of the trial, approval will be sought from a REC for the trial protocol, informed consent forms and other relevant documents e.g. advertisements and GP information letters. HRA approval will also be obtained.
- Substantial amendments that require review by REC will not be implemented until the REC grants a favourable opinion for the amendment and HRA amendment approval is received. Amendments may also need to be reviewed and accepted by the MHRA and/or NHS R&D departments before they can be implemented in practice at the site.
- All correspondence with the REC, MHRA and HRA will be retained in the Trial Master File.
- An annual progress report (APR) will be submitted to the REC within 30 days of the anniversary date on which the favourable opinion was given, and annually until the trial is declared ended.
- It is the Chief Investigator's responsibility to produce the annual reports as required.
- The Chief Investigator will notify the REC of the end of the trial.
- if the trial is ended prematurely, the Chief Investigator will notify the REC, including the reasons for the premature termination.
- Within one year after the end of the trial, the Chief Investigator will submit a final report with the results, including any publications/abstracts, to the REC.

13.2 Peer review

The study design has been reviewed and approved by multiple independent scientific/medical personnel on behalf of the British Heart Foundation, who also reviewed the statistical aspects.

13.3 Public and Patient Involvement

Members of the Sheffield Cardiovascular Patient Panel have been involved in reviewing the design of the study and key participant documents during development of this protocol and associated documentation.

13.4 Regulatory Compliance

- The trial will not commence until a Clinical Trial Authorisation (CTA) is obtained from the MHRA and Favourable REC opinion.
- The protocol and trial conduct will comply with the Medicines for Human Use (Clinical Trials) Regulations 2004 and any relevant amendments.
- No ionising radiation will be used during this study.

13.5 Protocol compliance

- Prospective, planned deviations or waivers to the protocol are not allowed under the UK regulations on Clinical Trials and must not be used e.g. it is not acceptable to enrol a participant if they do not meet the eligibility criteria or restrictions specified in the trial protocol.
- Accidental protocol deviations must be adequately documented on the relevant Sponsor-provided forms and reported to the Chief Investigator and Sponsor immediately.
- Deviations from the protocol which are found to frequently recur will require immediate action and could potentially be classified as a serious breach, at the discretion of the Sponsor.

13.6 Notification of Serious Breaches to GCP and/or the protocol

A “serious breach” is a breach which is likely to effect to a significant degree –

- (a) the safety or physical or mental integrity of the participants of the trial; or
- (b) the scientific value of the trial

The Sponsor will be notified immediately of any case where the above definition applies during the trial conduct phase

- The Sponsor will notify the licensing authority in writing of any serious breach of
 - (a) the conditions and principles of GCP in connection with that trial; or
 - (b) the protocol relating to that trial, as amended from time to time, within 7 days of becoming aware of that breach

13.7 Data protection and patient confidentiality

All investigators and trial site staff must comply with the requirements of the Data Protection Act 2018 with regards to the collection, storage, processing and disclosure of personal information and will uphold the Act’s core principles.

- Personal information will be collected by the investigators, kept secure within a room in the Cardiovascular Research Unit that is kept locked and alarmed out-of-hours, and will be maintained by the staff of the Cardiovascular Research Unit. This will involve:
 - Within the master trial database the creation of coded, depersonalised data whereby the participant's identifying information will be replaced by the study enrolment number.
 - Secure maintenance of the data and the linking code in separate locations using encrypted digital files within password protected folders and storage media on NHS or University of Sheffield computing systems.
 - Limiting access to the minimum number of individuals necessary for quality control, audit, and analysis.
- Monitoring visits will take place at site to avoid any data breaches. Transmission of information relating to safety eg. SAE reports will occur by secure NHS email channels. Any sharing of data with collaborators will be anonymised.
- Study source documents will be kept for a minimum of 15 years as per Sponsor protocols.
- The data custodian will be the CI.

13.8 Financial and other competing interests for the chief investigator, PIs at each site and committee members for the overall trial management

[name]: institutional research grants/support from AstraZeneca, and PlaqueTec; consultancy fees from Actelion, AstraZeneca, Avacta, Bayer, Bristol Myers Squibb, Novartis, PlaqueTec, Haemonetics and Thromboserin; speaker fees from AstraZeneca, and Bayer. Nominated by University of Sheffield as inventor on patent application related to concepts explored in this study.

[name]: nominated by University of Sheffield as inventor on patent application related to concepts explored in this study.

